9.3.3 Partial Response (PR) requires all of the following

- At least a less than or equal to a 30% decrease in sum of the product of the longest diameters (SLD) of up to three of the largest dominant nodes or nodal masses. These nodes or masses should be selected according to all of the following: they should be clearly measurable in at least two perpendicular dimensions; if possible, they should be from disparate regions of the body; and they should include mediastinal and retroperitoneal areas of disease whenever these sites are involved.
- 2. No increase should be observed in the size of other nodes, liver, or spleen.
- 3. Splenic and hepatic nodules must regress by 30% in their SLD or, for single nodules, in the greatest transverse diameter.
- 4. With the exception of splenic and hepatic nodules, involvement of other organs is usually assessable, and no measurable disease should be present.
- 5. Participants who achieve a CR by the above criteria, but who have persistent morphologic bone marrow involvement will be considered partial responders. When the bone marrow was involved before therapy and a clinical CR was achieved, but with no bone marrow assessment after treatment, participants should be considered partial responders.
- 6. No new sites of disease should be observed.
- 7. Typically FDG-avid lymphoma: for a participant with no pretreatment PET

scan or if the PET scan was positive before therapy, the post-treatment PET should be positive in at least one previously involved site.

8. Variably FDG-avid lymphomas/FDG-avidity unknown: if a pretreatment PET scan was negative, CT criteria should be used.

9.3.4 Minor Response (MR)

Minor Response (MR) is defined as the following A participant is considered to have MR when he or she fails to attain the criteria needed for a CR or PR, less than or equal to 10% decrease or less than or equal to 20% increase in the sum of longest diameters of the target lesions. Typically FGD-avid lymphomas: the PET should be positive at prior sites of disease with no new areas of involvement on the post-treatment CT or PET.

9.3.5 Stable Disease (SD) is defined as the following A participant is considered to have SD when he or she fails to attain the criteria needed for a CR or PR, <10% decrease or less than or equal to 20% increase in the sum of longest diameters of target lesions. Typically FGD-avid lymphomas: the PET should be positive at prior sites of disease with no new areas of involvement on the post- treatment CT or PET.

Variably FDG-avid lymphomas/FDG-avidity unknown: if the pretreatment PET was negative, there must be no change in the size of the previous lesions on the post-treatment CT scan.

9.3.6 Relapsed Disease (RD) (after CR)/Progressive Disease (PD) (after PR, SD)

Lymph nodes should be considered abnormal if the long axis is more than 1.0 cm regardless of the short axis. >20% increase in the sum of longest diameters of target lesions. For small lymph nodes measuring <15mm post-therapy, a minimum absolute increase of 5mm and the long diameter should exceed 15mm or the appearance of a new lesion will enough define the participant with RD or PD.

If a lymph node has a long axis of 1.1 to 1.5 cm, it should only be considered abnormal if its short axis is more than 1.0. Lymph nodes 1.0×1.0 cm will not be considered as abnormal for relapse or PD.

Appearance of any new lesion more than 1.5 cm in any axis during or at the end of therapy, even if other lesions are decreasing in size. Increased FDG uptake in a previously unaffected site should only be considered relapsed or progressive disease after confirmation with other modalities. In participants with no prior history of pulmonary lymphoma, new lung nodules identified by CT are mostly benign. Thus, a therapeutic decision should not be made solely on the basis of the PET without histologic confirmation.

- 9.3.7 *Recurrent Disease* is defined as the appearance of tumor following documentation of a complete remission.
- 9.3.8 *Time to Response* is defined as time from the first dose of chemotherapy until documentation of first response.
- 9.3.9 *Time to Progression* is defined as time from initiation of chemotherapy to documentation of first progression.

9.3.10 *Response Duration* is defined as the time from first documentation of response to documentation of first progression.

Table 6. Response Categories Based on Assessment of Target Lesions

% Change in sum of diameters of target lesions from nadir												
	CR	PR	MR	SD	PR							
% change from baseline	Complete disappear-ance of all target lesions and all nodes with long axis <10mm ≥30% decrease in the sum of longest diameters of target lesions (PR) with normaliza-tion of FDG-PET	≥30% decrease in the sum of longest diameters of lesions but not a CR	≥10% decrease in the sum of longest diameters of target lesions but not a PR (<30 %)	<10% decrease or ≤20% increase in the sum or the longest diameters of target lesions	>20% increase in the sum of longest diameters of target lesions For small lymph nodes measuring <15mm post-therapy, a minimum absolute increase of 5mm and the long diameter should exceed 15mm Appearance of a new lesion							
FDG-PET	Normalization of FDG-PET (Deauville score 1- 3)	Positive (Deauville score 4-5)	Any	Any	Any							
Bone marrow involvement	Not involved	Any	Any	Any	Any							
New lesions	No	No	No	No	Yes or No							

CR, complete response; CT, computerized tomography; FDG-PET, [18F]2-fluoro-2-deoxy-D-glucose; MR, minor response; PD, progression of disease; PR, partial response; SD, stable disease.

10.0 STATISTICAL CONSIDERATIONS

10.1 Study Design/Endpoints

This is a phase I dose de-escalation trial of ipilimumab and nivolumab in advanced HIVassociated solid tumors implemented as a rolling six design that first establishes the MTD for single agent nivolumab and then the MTD for combination of ipilimumab and nivolumab. Since there are only two dose levels within each single and combination therapy, the design requires the full cohort of six participants be enrolled unless two or more experience a DLT. The design is stratified by lymphocyte T CD4+ count (above 200/mm³ for Stratum 1 and 100-200/mm³ for Stratum 2). Please see Section 4.2 and Section 4.3 of the Treatment Plan for the dose levels of ipilimumab and nivolumab, and Section 4.4 for the definition of DLT. After the combination therapy MTD has been determined, an expansion cohort in HIV-associated solid tumors will be enrolled. An expansion cohort in solid tumors, excluding those histologies not known to respond to single agent nivolumab (i.e. pancreas, prostate, MSS colorectal cancer) with CD4 counts > 200/mm³ will also be enrolled and treated with single agent nivolumab. An additional cohort of participants with relapsed refractory cHL will be treated with single agent nivolumab. No intra-participant dose escalations will be allowed. Overall study duration including completion of evaluation of the final participant is projected to be 5 years.

10.1.1 Primary endpoints

Dose De-Escalation Strata: To demonstrate safety and feasibility of ipilimumab and nivolumab at the standard doses of drug in solid tumor participants with HIV infection given the possibility of increased toxicity based on immune activation, co-morbidity, or interference with HAART therapy. The purpose for this would be to provide appropriate experience and guidelines, if necessary, to allow participants with HIV infections to participate in ongoing trials.

10.1.2 Analysis of primary objective

Please see Section 4.2 of the Treatment Plan for the dose de-escalation decision rule. In summary, the primary goal in this phase I study is to determine the safety and feasibility of ipilimumab and nivolumab in combination therapy in participants with advanced HIV-associated solid tumors, and to determine the maximum tolerated dose (MTD) in this participant population. A rolling design will be used, where successive cohorts of two to six participants will be enrolled into specified dose levels. Dosing from nivolumab alone to nivolumab in combination with ipilimumab will occur according to the scheme in the treatment plan; the safety evaluation period is 6 weeks. The MTD for single agent or combination therapy is the starting dose level at which $\leq 1/6$ participants experience DLT with the next higher dose having at least >2 participants encountering DLT (unless the MTD is the highest pre-specified dose level). DLTs for this protocol are defined in Section 4.4. Given the potential susceptibility of participants with CD4+ counts \(\leq 200 \)/mm³, the dose de-escalation will initially occur in participants with counts >200/mm³ (Stratum 1), and then participants in Stratum 2 (100-200/mm³ CD4 counts) will be evaluated starting at the MTD determined in Stratum 1 after reviewing the safety profile for Stratum 1. For Stratum 2, participants will be enrolled starting at the Stratum 1 DLT in cohorts of 2-6 participants. Stratum 2 participants will not be

allowed to escalate beyond the MTD for Stratum 1; one dose level de-escalation will be allowed based on the criteria in the treatment plan.

If a DLT occurs in none or one participant in Stratum 1 at a particular dose level, a total of six participants will be enrolled to that cohort. If a second participant experiences a DLT, the MTD will have been exceeded. If 2 DLTs are experienced at the first cohort, one dose de-escalation (Dose Level -1) will be permitted according to the study schema in the treatment plan. Similarly, if 2 DLTs are experienced at dose level 2, a dose de-escalation (Dose Level -2) will be permitted. Thus, the MTD is the dose level at which $\leq 1/6$ participants experience DLT with the next higher dose having ≥ 2 participants encountering DLT (unless the MTD is the highest pre-specified dose level) during the safety evaluation period.

To better estimate the preliminary efficacy of treatment, an expansion cohort of 12 participants will be treated at the MTD for single agent nivolumab or combination therapy with ipilimumab and nivolumab (depending on the results of the Phase I portion). If the MTDs differ between the two strata then there will be two expansion cohorts of 18 participants with a CD4 count >200 cells/mL and six participants with a CD4 count between 100 and 200 cell/mL. Also, to better estimate preliminary safety (secondary objective) in HIV infected individuals, a cohort of 24 participants with solid tumors (excluding histologies not known to respond to single agent nivolumab) and a cohort of 12 participants with cHL will be treated with single agent nivolumab.

All participants will be evaluable for toxicity from the time of nivolumab (which is administered first when there is concurrent treatment with ipilimumab). The details of toxicity grading and reporting may be found in Section 6.0. Toxicity data will be presented by type and severity for each dose group and overall; the incidence of toxicity related dose reductions and treatment discontinuations will be summarized.

10.2 Sample Size/Accrual Rate

For phase I, Stratum 1, a minimum of four to a maximum of 18 participants will be enrolled. For phase I, Stratum 2, a minimum of zero to a maximum of 18 participants will be enrolled. An expansion cohort of 24 participants will be treated at the combination therapy MTD, and an expansion cohort of 24 participants with solid tumors, excluding those histologies not known to respond to single agent nivolumab (i.e. pancreas, prostate, MSS colorectal cancer) will be treated with single agent nivolumab. Also, 12 participants with relapsed refractory cHL will be treated with single agent nivolumab. Therefore, in total, this study will enroll a minimum of four participants and a maximum of 96 participants.

Considering precision, 12 participants in the additional cHL cohort would yield an exact 95% confidence interval of 38% to 92% when the ORR is 70%, and 24 participants in the additional solid tumor cohort would yield an exact 95% confidence interval of 48% to 87%, such that these estimates would be considered preliminary.

Accrual will be approximately two participants per month for phase I, Stratum 1; approximately one participant per month for phase I, Stratum 2; and approximately 2-3 participants per month for each of the two solid tumor expansion cohorts. And, 3-4 participants per month for the cHL cohort.

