The combination therapy MTD will then be studied in a dose expansion cohort (12 participants) limited to only participants with Kaposi sarcoma, lung cancer, and anal cancer; CD4+ count eligibility criteria in the expansion cohort will be determined after reviewing results from Strata 1 and 2. If the MTDs differ between the two strata, expansion cohorts of six participants each will be enrolled. The study treatment consists of 12 IV infusions of nivolumab, 240 mg, on Day 1 of each 2-week cycle and ipilimumab on Day 1 every 6 weeks with four total ipilimumab doses, i.e., every third cycle (cycles 1, 4, 7, 10). After completion of the 12th cycle of nivolumab, the nivolumab dose will change to a flat dose of 480mg, on Day 1 of each 4-week cycle without ipilimumab. Participants with an overall response of SD, PR, CR, or unconfirmed PD at Week 8 will continue treatment (Refer to Section 9.1 for RECIST Criteria) for up to 84 weeks.

A single agent expansion cohort of 24 participants with solid tumors, excluding those histologies not known to respond to single agent nivolumab (i.e., pancreas, prostate, and microsatellite stable [MSS] colorectal cancer) and with CD4 count above 200 will receive single agent nivolumab at 240mg administered every 2 weeks for up to 46

^{**} After evaluating single agent nivolumab dosing, the next dose level will be 2 if dose level 1 is the MTD for single agent nivolumab and dose level -2 if dose level -1 is the single agent MTD. It is also possible to de-escalate from dose level 2 to -2.

doses, or until disease progression, toxicity, study termination, or study withdrawal.

Another single agent cohort of 12 participants with relapsed refractory HIV-associated cHL and with CD4 counts ≥ 100/mm³, will also be treated with single agent nivolumab at a flat dose of 240mg administered every 2 weeks for 46 doses or until disease progression, toxicity, study termination, or study withdrawal (See Section 9.3 for the 2017 response evaluation criteria in lymphoma (RECIL) Criteria for evaluation of measurable disease in HIV-cHL and Section 4.7 and 4.9 for study duration and criteria for removal from study). Participants with an overall response of SD, PR, CR, or unconfirmed PD at Week 8 will continue treatment. Of note, this dose showed no dose-limiting toxicity (DLT) in this trial and is the current FDA approved dosing regimen for non-HIV classical Hodgkin lymphoma.

Duration: Maximum of 92 weeks of treatment

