4.0 TREATMENT PLAN

4.1 Treatment Design

Protocol agents will be administered on an outpatient basis. Reported AEs and potential risks for ipilimumab and nivolumab are described in Section 6.0. Appropriate dose modifications for ipilimumab and nivolumab are described in Section 5.0, Appendix X. No investigational or commercial agents or therapies other than those described below may be administered with the intent to treat the participant's malignancy.

Participants will be studied in separate strata. Stratum 1 will enroll participants with lymphocyte T CD4+ count above $200/\text{mm}^3$. Stratum 2 will enroll participants with lymphocyte T CD4+ count between $100\text{-}200/\text{mm}^3$. Enrollment on Stratum 2 will occur sequentially, initially in Stratum 1 at dose level 1, and then in Stratum 2 after Stratum 1 has completed and an MTD has been determined. Once the MTD is determined in each stratum, the MTD will then be studied in a dose expansion cohort of up to 12 participants. If the MTDs differ between the two strata, expansion cohorts of six participants each will be enrolled. An additional cohort of 12 participants with cHL and lymphocyte T CD4+ count $\geq 100/\text{mm}^3$ will be treated with single agent nivolumab. Lastly, an additional 24 participants with solid tumors will be treated with single agent nivolumab.

4.2 Dose De-Escalation Cohorts: Stratum 1 and Stratum 2

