4.2.3 Expansion Cohort in Solid Tumors and Lymphoma

An additional 24 participants with incurable solid tumors will be treated at the MTD, according to the treatment schedule defined above for each stratum. If the MTDs differ between the two strata, expansion cohorts of six participants each will be enrolled.

Another 24 participants with incurable solid tumors will be treated at single agent nivolumab 240 mg every 2 weeks. Only those histologies that are not known to respond to single agent nivolumab will be excluded (i.e., pancreas, prostate, MSS colorectal cancer, unless results from another clinical trial showing non-response in another tumor type become available in the future).

Participants with HL will be treated at the FDA approved flat dose of 240mg given every 2 weeks.

Participants with an overall response of SD, PR, CR, or unconfirmed PD at the end of the first four cycles of nivolumab will continue treatment for up to a total of 46 cycles of nivolumab (with ipilimumab if receiving dose level 2 or -2) (refer to Section 9.1 for RECIST Criteria and Section 9.3 for the 2017 response evaluation criteria in lymphoma (RECIL) Criteria for evaluating measurable disease in HIV-cHL).

Participants with a confirmed PD will discontinue the study drugs.

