4.3.3 Stratum 2 treatment

Stratum 2 dosing will begin based on the single agent therapy MTD determined in Stratum 1. Stratum 2 will not be allowed to escalate beyond the MTD for Stratum 1. An expansion cohort will be treated at the MTD for Stratum 1. If the MTDs differ between the two strata, expansion cohorts of six participants each will be enrolled.

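### The combination expansion cohort is planned at 12 in three places and 24 in two, with two incompatible splits, and the stated maximum of 96 is reached only with 24

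*Combined protocol and SAP*

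**What the plan says.** **Size.** The synopsis (Regimen) describes a "dose expansion cohort (12 participants) limited to only participants with Kaposi sarcoma, lung cancer, and anal cancer". Section 4.1 says "the MTD will then be studied in a dose expansion cohort of up to 12 participants". Section 10.1.2 says "To better estimate the preliminary efficacy of treatment, an expansion cohort of 12 participants will be treated at the MTD". Against these, Section 4.2.3 says "An additional 24 participants with incurable solid tumors will be treated at the MTD", and Section 10.2 says "An expansion cohort of 24 participants will be treated at the combination therapy MTD".

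**Split if the stratum MTDs differ.** Section 4.3.3 says "If the MTDs differ between the two strata, expansion cohorts of six participants each will be enrolled". The synopsis, Section 4.1 and Section 4.2.3 say the same. Section 10.1.2 instead gives "two expansion cohorts of 18 participants with a CD4 count >200 cells/mL and six participants" with CD4 100 to 200, and a Protocol Schema footnote also gives 18 and 6.

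**Total.** The maximum of 96 appears in the synopsis (Accrual Target), Section 3.4.1 (which refers to 10.2), Section 10.2 and Table 7 in Section 12.3.

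**Who may enter.** The synopsis limits this cohort to three tumor types. Section 3.3 opens the expansion to all solid tumors except known non-responders, without saying which solid tumor cohort it means. Section 4.2.3 refers only to incurable solid tumors, and Section 3.1.1 sets no histology limit for this cohort.

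**The concern.** The conflict lies between the treatment plan and the sample size section, and also inside the statistical section, because 10.1.2 and 10.2 disagree. A site following 4.1 would stop at 12. A site following 10.2 would count a 13th participant as within plan. Section 4.2.3 pairs a cohort of 24 with a split that accounts for only 12.

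At stake are the number of people treated with the combination in expansion, the safety data they provide, the precision of the combination response rate, and the meaning of the total of 96. Section 10.2 gives no precision statement for this cohort that would indicate which size was meant.

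**Working it through.** **1. Reproduce the total.** Inputs from Section 10.2: Stratum 1 maximum 18, Stratum 2 maximum 18, single agent solid tumor cohort 24, cHL cohort 12. The 18 per stratum agrees with the rules in Section 4.2: the longest path visits three dose levels of six, 3 × 6 = 18.

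- Combination cohort of 24: 18 + 18 + 24 + 24 + 12 = 96, the stated figure.
- Combination cohort of 12: 18 + 18 + 12 + 24 + 12 = 84.
- Solving for the cohort: 96 − 18 − 18 − 24 − 12 = 24.

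**2. Set the passages side by side.**

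| Place | Size | Split if MTDs differ | Split sums to |
|---|---|---|---|
| Synopsis, Regimen | 12 | 6 + 6 | 12 |
| Protocol Schema footnote | not in the text | 18 + 6 | 24 |
| 4.1 | up to 12 | 6 + 6 | 12 |
| 4.2.3 | 24 | 6 + 6 | 12 |
| 4.3.3 | not given | 6 + 6 | 12 |
| 10.1.2 | 12 | 18 + 6 | 24 |
| 10.2 | 24 | not given | – |

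The 24 is not a mix-up with the single agent solid tumor cohort. The synopsis and Sections 4.1, 4.2.3, 10.1.2 and 10.2 each list those 24 participants separately.

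**3. Accrual time.** At 2 to 3 per month (Section 3.4.2): 12/3 to 12/2 = 4 to 6 months; 24/3 to 24/2 = 8 to 12 months.

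**4. Safety information.** The chance of at least one case is 1 − (1 − p)^n. The true rates p are assumed, because the protocol gives none.

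| Assumed p | n = 12 | n = 24 |
|---|---|---|
| 5% | 1 − 0.95^12 = 46% | 1 − 0.95^24 = 71% |
| 10% | 1 − 0.90^12 = 72% | 1 − 0.90^24 = 92% |

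This uses the expansion cohort alone, which gives the largest contrast. Section 10.1.2 says "Toxicity data will be presented by type and severity for each dose group and overall", but does not say whether the revised expansion schedule (Section 2.3.9) counts as its own dose group. If de-escalation participants on the combination are added, I assume 6 to 18 of them: one full Stratum 1 cohort of six, plus 0 to 12 from Stratum 2. The total is then 18 to 30 with a cohort of 12, against 30 to 42 with 24. At 5% the chance is 60–79% against 79–88%; at 10% it is 85–96% against 96–99%.

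**5. Response rate.** Exact 95% intervals at an assumed observed rate of 50%:

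| Basis | Cohort of 12 | Cohort of 24 |
|---|---|---|
| Expansion alone | 6/12: 21–79% | 12/24: 29–71% |
| Pooled with 6 | 9/18: 26–74% | 15/30: 31–69% |
| Pooled with 18 | 15/30: 31–69% | 21/42: 34–66% |

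Section 10.4.1 pools expansion and de-escalation participants, so the lower two rows are the planned analysis. From unrounded limits, the interval narrows from 48.0 to 37.4 points in one case and from 37.4 to 31.6 in the other.

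**The case against.** The strongest reply is that Section 10.1.2 contains a conditional rule: 12 if the MTDs agree, two cohorts of 18 and six if they differ. Section 10.2 adds maxima, so 24 could be the larger of the two cases and 96 a true ceiling. This reading stands as a possibility, and it means that 10.1.2 need not contradict itself. It does not remove the conflict. Section 10.2 states 24 without that condition, the synopsis and 4.1 stay at 12 in both cases, and 4.2.3 gives 24 and then splits it six and six.

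It is also fair that the consequence is limited. The response rate is a preliminary, descriptive secondary outcome, and pooling narrows the difference.

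Three stronger readings are tempting but unsupported:

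- **That 24 must be the intended size.** The sum shows that 96 was built with 24. It does not show what the sponsor now intends, and no precedence rule overrides the sections that say 12.
- **That 12 rules out the disease-specific estimates.** More than five in each of Kaposi sarcoma, lung and anal cancer does need 3 × 6 = 18 in the expansion cohort alone. But 10.4.1 pools de-escalation participants and does not require all three histologies; six and six in two of them would qualify two. Objective 1.2.2 also covers the single agent cohort.
- **That the plan contradicts itself on whether this cohort's safety is primary or secondary.** The secondary-objective label in 10.1.2 attaches to the single agent solid tumor and cHL cohorts, not to this one.

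**Conclusion.** The point holds for size and split. The cohort's planned number differs twofold between sections, two incompatible splits are given, and the stated maximum adds up only with 24 (84 with 12). Where the cohort closes depends on the section read.

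The error does not reach any test, stopping rule or MTD decision. Its effect is on how much combination safety data is collected and, modestly, on the precision of the combination response rate. These sizes rest on assumed toxicity rates of 5% and 10%, an assumed observed response rate of 50%, and 6 to 18 pooled de-escalation participants. The sums rest on the documents alone, and leave out participants replaced under Section 4.2.

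The histology passages for this cohort also conflict. Another schema footnote places expansion at the Stratum 1 dose in participants with CD4 above 200 when the combination MTDs differ. The schema figure is not shown, so that footnote needs checking but cannot be called an error.

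**What to change.** State one size and one split in every section. There are three coherent options, and the sponsor must say which is intended.

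1. **24, split 18 + 6.** Correct the synopsis, 4.1, 4.2.3, 4.3.3 and 10.1.2. Also reword the labels that identify the single agent cohort by its size of 24 (the schema note, 3.1.1 and the note under Table 1 in 4.2), since two cohorts would then have that size. The maximum of 96 stands.
2. **12, split 6 + 6.** Correct the schema footnote, 4.2.3, 10.1.2 and 10.2. Restate the maximum as 84 in the synopsis, 3.4.1, 10.2 and Table 7.
3. **12 if the MTDs agree, 18 + 6 if they differ.** State the condition in the synopsis, 4.1, 4.2.3, 4.3.3 and 10.2, and describe 96 as the maximum when the MTDs differ.

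In the same revision, reconcile the histology text in the synopsis, 3.1.1, 3.3 and 4.2.3 so that one rule names this cohort, and check the CD4 footnote in the schema against the chosen split.

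Cost: one protocol amendment, which Section 12.2 requires for any change. No option needs more than 96 participants. Option 1 raises the cap in 4.1, option 2 lowers planned enrolment by 12, and settling the histology rule changes eligibility text, so none of these is purely editorial.
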